9.4.5 BASELINE DESCRIPTIVE STATISTICS

Descriptive statistics (e.g., means standard deviations, medians, counts, and percentages), will be used to describe the study cohort. No inferential statistical testing will be performed.

9.4.6 PLANNED INTERIM ANALYSES

No interim analysis is planned.

9.4.7 SUB-GROUP ANALYSES

The primary and secondary endpoints will be analyzed by sex and by presence or absence of select NAFLD genes which may alter response to the IP. Differences in the primary outcome (% change in ALT from Baseline to Week 12) will be compared among sexes and genetic subgroups using two-sample t-

tests or Wilcoxon rank sum tests, as applicable. Percent change for other continuous measures will be analyzed similarly. For subgroups with more than two levels, we will test for differences in percent change from baseline using analysis of variance (ANOVA) models with a Tukey-Kramer post-hoc multiple comparison procedure or a Kruskal Wallis test with a Dwass, Steel, Critchlow-Fligner multiple comparison procedure.

For raw changes in continuous measures (ALT, AST, etc.) subgroup analysis will be conducted using analysis of covariance (ANCOVA) models. Specifically, for each outcome of interest, we will compare the 12-week outcome measure between subgroups (e.g., sex) controlling for the baseline value of the outcome measure. Initial models will include the interaction between subgroup and baseline value to assess the homogeneity of slope assumption. If the assumption is met, the interaction will be removed and least square means with associated 95% confidence intervals will be provided for each subgroup. Differences in subgroup means will be reported and accompanied by 95% confidence intervals. If the assumption of homogeneity of slopes is violated, an alternative approach such as the Johnson-Neyman procedure, will be utilized.

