9.2 SAMPLE SIZE DETERMINATION

The sample size for this study is 36 completed participants. A percent change from baseline of approximately 20% is considered to be clinically meaningful. Assuming a two-sided test at the 5% significance level, 36 completed participants will provide 81% power to detect a percent change from baseline of 20% (effect size = 0.5), if the standard deviation is 40%. Additionally, assuming a drop-out rate of 10%, a total of 40 participants is needed for enrollment into the study to ensure an adequate number of subjects complete the trial. Power was calculated using a two-sided Wilcoxon test with a 0.05 significance level using PASS v. 14.0.8 (Kaysville, UT).

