9.4 STATISTICAL ANALYSES

9.4.1 GENERAL APPROACH

Statistical significance will be assessed at the 0.05 level, unless otherwise noted.

Descriptive statistics will be calculated for all variables of interest and include means and standard deviations or medians and ranges (for continuous measures) or counts and percentages (for categorical measures), as appropriate. Continuous data will be assessed for normality using histograms and normal probability plots and statistically tested using the Anderson-Darling test and/or the Shapiro Wilk test for normality. Non-normal data will be presented using medians accompanied by 25th and 75th. All analyses will be conducted using SAS v. 9.4 (Cary, NC) or CRAN R v. 3.3 (Vienna, Austria).

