9.4.9 EXPLORATORY ANALYSES

Exploratory analyses are planned as described in the sub-study (appendix A).

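### Section 9.4.7 compares every endpoint by sex and by an unlisted set of genes at the default 0.05, with no adjustment and no exploratory label, in about 36 children

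*Combined protocol and SAP*

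**What the plan says.** Section 9.4.7 sets the scope: "The primary and secondary endpoints will be analyzed by sex and by presence or absence of select NAFLD genes which may alter response". For the primary outcome, percent change in ALT to Week 12, values "will be compared among sexes and genetic subgroups using two-sample t"-tests or rank-sum tests. It then adds: "Percent change for other continuous measures will be analyzed similarly". Raw change is compared by ANCOVA on the Week 12 value with baseline as covariate, after a check for a subgroup-by-baseline interaction.

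Section 9.4.1 gives the level: "Statistical significance will be assessed at the 0.05 level, unless otherwise noted". Section 9.4.7 notes no other level. Its one multiplicity provision (Tukey-Kramer, or Dwass-Steel-Critchlow-Fligner after a Kruskal-Wallis test) covers pairs of levels within a single factor that has more than two levels.

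Section 9.4.7 does not describe its tests as exploratory. Section 9.4.9 reads: "Exploratory analyses are planned as described in the sub-study (appendix A").

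DNA is collected at Screening (Table 2). Treatment is open label (section 6.3). Local ALT is measured at each clinic visit and reviewed by study staff, while central ALT is assayed in one batch after all visits are complete (Table 2, section 8.1).

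**The concern.** Each subgroup factor is crossed with a long list of endpoints, and every comparison is judged at 0.05. The number of factors is open, so the size of the family is not fixed in advance. Because local ALT is visible during an open-label trial and DNA is already banked, the genes could be chosen after responses are known.

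The sample was sized for one overall change from baseline and not for a difference between two parts of the sample. A plan with many comparisons and little power for each will tend to produce some nominally significant differences, and those that appear will be large because only large estimates can cross the threshold. Section 2.2 says the trial will support later phase 2b and phase 3 trials. A sex or genotype difference reported as significant could influence whom those trials enrol.

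**Working it through.** **1. The plan's own figure.** Section 9.2 states: "36 completed participants will provide 81% power to detect a percent change from baseline of 20% (effect size = 0.5), if the standard deviation is 40"%. It also says: "Power was calculated using a two-sided Wilcoxon test with a 0.05 significance level using PASS". For a one-sample two-sided test with effect size 20/40 = 0.5 and n = 36, the noncentral t gives 83.1%. With the Wilcoxon efficiency, n × 3/π = 34.4, it gives 81.2%, and simulating the signed-rank test gives 81.7%. The stated 81% reproduces. So does the enrolment figure, "assuming a drop-out rate of 10%, a total of 40 participants is needed for enrollment": 36/0.9 = 40. No error rate or power is stated for the subgroup tests.

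**2. Number of measures.** Tally from section 3, main study only, one Week 12 comparison on one scale per measure:

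- ALT, AST, GGT: 3
- liver and pancreatic fat: 2
- insulin, glucose, HOMA-IR: 3
- lipids: 6
- apolipoproteins: 5
- inflammatory markers: 4
- particle sizes: 4
- LIF and cT1: 2
- body composition: at least 1
- anthropometry: 4

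The total is 34. It leaves out Week 6, the second scale, the slope-interaction tests and the sub-study measures (taken in 10 children), so the full number of tests is larger.

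**3. False positives over the family.** If there is no true subgroup difference, the expected number is 0.05 × 34 = 1.7 per factor, whatever the correlation. For sex plus two genes it is 0.05 × 102 = 5.1. With independent tests, the chance of at least one is 1 − 0.95^34 = 82.5% for sex alone and 1 − 0.95^102 = 99.5% for sex plus two genes. For correlated measures, two-sample t-tests were simulated in 36 children (sex split 18/18, genes 14/22):

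| Correlation between measures | Sex alone | Sex + 2 genes |
|---|---|---|
| 0 (formula) | 82.5% | 99.5% |
| 0.3 | 71% | 97% |
| 0.5 | 54–56% | 90% |
| 0.8 | about 27% | about 60% |
| 0.5 within a domain, 0.1 between | 76% | 98% |

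The documents give neither the number of genes nor the correlations. Both are assumptions. Two genes is the smallest number consistent with the plural in section 9.4.7.

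**4. Primary endpoint alone.** With sex plus k genes, one independent test each, the chance is 1 − 0.95^(k+1): 5.0% (k = 0), 9.8% (k = 1), 18.5% (k = 3), 26.5% (k = 5).

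**5. Power for a subgroup difference.** Using the plan's SD of 40% and 36 completers, two-sided 0.05, noncentral t:

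| Split | Power for a 20-point difference | Difference detectable with 80% power |
|---|---|---|
| 18 v 18 | 31% | 38.5 points |
| 24 v 12 | 28% | 41 points |
| 27 v 9 | 24% | 44.5 points |

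**6. Inflation.** At 18 v 18 the standard error of the difference is 40 × √(2/18) = 13.3 points. With a critical t of 2.03 on 34 degrees of freedom, an observed difference must reach about 2.03 × 13.3 = 27 points to be significant when the sample SD is 40. If the true difference is 10 points, power is 11% and the significant estimates average about 32 points in absolute size.

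**The case against.** The trial is an open-label proof-of-concept study of preliminary efficacy. None of the critical questions in section 2.2 concerns sex or genotype, and no decision rule or enrichment plan depends on a subgroup result. The primary inference is untouched. Section 9.4.7 already plans 95% confidence intervals for subgroup differences in raw change. All of this stands, and it lowers the stakes. It does not remove the rule that each comparison is judged at 0.05, and the primary scale, percent change, has no planned interval for the subgroup difference.

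Three stronger readings are tempting, and the documents do not support them.

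- A reader might infer that chance subgroup findings are near certain. That needs at least two genes and correlation that is not extreme. It does not describe sex, the only named factor, on its own, and it does not describe the primary endpoint alone.
- A reader might infer from section 9.4.9 that everything outside Appendix A is meant as confirmatory. That section is not an exhaustive list: section 2.2 also calls work on ketogenesis and metabolomics exploratory, and neither is in Appendix A. What holds is that section 9.4.7 itself carries no such label.
- A reader might infer that a significant subgroup result would very probably be false. That depends on the prior. With 11% power (a true 10-point difference) and 5% error, such a result would be real about 20%, 36% or 69% of the time at assumed priors of 10%, 20% or 50%.

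**Conclusion.** The concern holds as a fault in a stated rule. Section 9.4.7 puts the primary and all secondary endpoints through comparisons by sex and by an open set of genes. The default 0.05 applies to each, with no adjustment across factors or endpoints and no statement that the tests are exploratory.

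Followed as written over about 34 measures, this yields about 1.7 chance differences per factor. At least one would be likely for sex alone and very likely for sex plus two genes at correlations up to 0.5, and clearly less so at 0.8. For the primary endpoint alone the risk is modest. The subgroup comparisons are weak at the plan's own SD, so a nominally significant result would be unreliable or inflated.

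The sizes rest on the tally of 34 measures, the assumed number of genes, the correlations, the subgroup splits and 36 completers. The problem affects how subgroup results are reported and used. It does not affect the overall test of percent change in ALT.

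**What to change.** In section 9.4.7:

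1. State that all subgroup analyses are exploratory and exempt from the 0.05 rule of section 9.4.1.
2. Report between-subgroup differences with 95% confidence intervals for percent change as well as raw change, with no claim of significance.
3. List the genes or variants and their coding before any genotype data are linked to any ALT result, local or central. Fixing the list only before the central assay would leave the choice open, because local ALT is seen at each clinic visit.
4. If a p-value is quoted for the primary endpoint by subgroup, give with it the number of subgroup factors tested, or a Holm-adjusted value across sex and the listed genes.

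This changes SAP wording and table layout only. It needs no new participants, samples or visits. The downside is that no subgroup effect can be declared significant.

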9.4.8 TABULATION OF INDIVIDUAL PARTICIPANT DATA

N/A

9.4.9 EXPLORATORY ANALYSES

Exploratory analyses are planned as described in the sub-study (appendix A).

10 SUPPORTING DOCUMENTATION AND OPERATIONAL CONSIDERATIONS

10.1 REGULATORY, ETHICAL, AND STUDY OVERSIGHT CONSIDERATIONS

10.1.1 INFORMED CONSENT PROCESS

10.1.1.1 CONSENT/ASSENT AND OTHER INFORMATIONAL DOCUMENTS PROVIDED TO PARTICIPANTS

Consent and assent forms describing in detail the study intervention, study procedures, and risks are given to the participant and written documentation of informed consent is required prior to starting intervention/administering study intervention. The following consent materials are submitted with this protocol.

The following questionnaires and handouts will be submitted with the IRB submission:

- AUDIT questionnaire
- Block physical activity questionnaire
- Bev Q survey
- Food frequency questionnaire
- TANNER screener

- PROMIS Questionnaires (Fatigue, Anxiety, Depression)
- AHA Healthy Children Handout

10.1.1.2 CONSENT PROCEDURES AND DOCUMENTATION

Informed consent is a process that is initiated prior to the individual's agreeing to participate in the study and continues throughout the individual's study participation. Consent forms will be Institutional Review Board (IRB)-approved and the participant will be asked to read and review the document. The investigator will explain the research study to the participant and answer any questions that may arise. A verbal explanation will be provided in terms suited to the participant's comprehension of the purposes, procedures, and potential risks of the study and of their rights as research participants. Participants will have the opportunity to carefully review the written consent form and ask questions prior to signing. The participants should have the opportunity to discuss the study with their family or surrogates or think about it prior to agreeing to participate. The participant will sign the informed consent document prior to any procedures being done specifically for the study. Participants must be informed that participation is voluntary and that they may withdraw from the study at any time, without prejudice. A copy of the informed consent document will be given to the participants for their records. The informed consent process will be conducted and documented in the source document (including the date), and the form signed, before the participant undergoes any study-specific procedures. The rights and welfare of the participants will be protected by emphasizing to them that the quality of their medical care will not be adversely affected if they decline to participate in this study.

10.1.2 STUDY DISCONTINUATION AND CLOSURE

This study may be temporarily suspended or prematurely terminated if there is sufficient reasonable cause. The DSMB will review all AEs and SAEs and may suspend or terminate the study for safety concerns. AEs will be reviewed quarterly and for any SAE, an ad hoc meeting of the DSMB will be convened within 10 business days to review the event.

Written notification, documenting the reason for study suspension or termination, will be provided by the suspending or terminating party to study participants, investigators, Gemphire, the Investigational New Drug (IND) sponsor and regulatory authorities. If the study is prematurely terminated or suspended, the Principal Investigator (PI) will promptly inform study participants, the Institutional Review Board (IRB), and sponsor and will provide the reason(s) for the termination or suspension. Study participants will be contacted, as applicable, and be informed of changes to study visit schedule.

Circumstances that may warrant termination or suspension include, but are not limited to:

- Determination of unexpected, significant, or unacceptable risk to participants
- Demonstration of efficacy that would warrant stopping
- Insufficient compliance to protocol requirements
- Data that are not sufficiently complete and/or evaluable
- Determination that the primary endpoint has been met
- Determination of futility

Study may resume once concerns about safety, protocol compliance, and data quality are addressed, and satisfy the sponsor, IRB and/or Food and Drug Administration (FDA).

Patient-specific trial stopping rules include:

- In any patient who develops an AE of grade 3 that is probably or possibly related to study drug and any patient who develops a grade 4 or higher CTCAE regardless of causality assessment, investigational product will be discontinued.
- Hemoglobin will be assessed by central laboratory evaluation. For a hemoglobin decrease of > 1.5 g/dL from baseline during the study, repeat hematology studies and reflexive evaluation of reticulocyte count will be performed. The patient's past medical history, concomitant medications (including over the counter drugs and herbal supplements), and any recent symptoms (e.g., bleeding, shortness of breath, fatigue) will be reviewed to determine a potential etiology and make a clinical assessment of the significance of the finding.
- If hemoglobin falls >3.0 g/dL without any clear cause, then the investigator should discontinue the investigational product and hemoglobin should be monitored until it returns to a level of no less than 1.0 g/dL below baseline. At this time, the investigator can consider restarting the investigational product and recheck hemoglobin levels one and two weeks after re-initiation of investigational product. If hemoglobin levels decrease >3 g/dL again, investigational product should be discontinued and the subject should continue with all other study procedures. Hemoglobin should continue to be monitored until it returns to a level of no less than 1.0 g/dL below baseline.
- If, at any visit, a creatinine increase of > 0.3 mg/dL (27 μ mol/L) from baseline, a GFR decrease of > 15 mL/min from baseline, or a > 30 urinary albumin:creatinine ratio mg/g is observed, a repeat chemistry/urinalysis will be performed within one week. The patient's past medical history, concomitant medications (including over the counter drugs and herbal supplements), and any recent symptoms (e.g., fatigue, malaise, polyuria/oliguria, or palpitations) will be reviewed to determine a potential etiology and make a clinical assessment of the significance of the finding.
- Patients with persistent serum creatinine changes of > 0.3 to < 0.5 mg/dL will be evaluated by the investigator to determine if the subject has any signs and symptoms of renal injury. If the investigator determines that the biomarkers along with the signs and symptoms are consistent with renal injury, then investigational product should be discontinued, and the subject should continue with all future protocol assessments.
- If at any time there is a doubling of serum creatinine or a decrease > 50% in GFR from baseline, then investigational product should be discontinued immediately. The patient will be followed until renal parameters return to baseline or normal levels. The investigator can determine based on signs, symptoms and laboratory data whether or not to reinitiate investigational product and continue with scheduled monitoring. Regardless of whether or not investigational product is reinitiated subjects should continue with all future protocol assessments.

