2.3 RISK/BENEFIT ASSESSMENT

2.3.1 KNOWN POTENTIAL RISKS

The safety and efficacy profile of gemcabene has been developed through 18 Phase 1 and 2 studies including 1278 healthy volunteers and patients.

Common adverse events include:

- Headaches
- Asthenia (feeling of weakness)
- Nausea
- Dizziness
- Dyspepsia
- Abnormal bowel movements
- Myalgia (muscle pain)
- Increased BUN
- Increased creatinine

Identified and Potential Important Risks:

Based on the non-clinical and clinical safety data collected, important potential risks are liver findings, hemoglobin decrease, BUN and creatinine increase and myalgia. Importantly, only one patient had transaminase elevation > 3x ULN after receiving gemcabene 600 mg and atorvastatin 80 mg and the

percentage of transaminase elevations overall is similar to placebo. While hemoglobin decrease was seen in non-clinical toxicity studies, only small decreases in hemoglobin have been observed clinically and were also seen with placebo (not statistically significant). Small increases in creatinine and BUN have been observed in clinical studies with gemcabene. The effects were mild and appeared within the first 2-4 weeks of treatment, did not worsen over time and were not persistent and generally resolved within 10-14 days after discontinuation of gemcabene.

Other risks:

- There is a possibility of rhabdomyolysis when combined with a statin.
- Patients with a hypersensitivity to or who have a history of significant adverse reactions to any fibrate lipid lower agents should avoid gemcabene.
- Patients on potent CYP 3A4 inhibitors such as itraconazole or a macrolide antibiotic should be excluded.
- Based on non-clinical studies in rats, gemcabene should not be administered to pregnant women or women of childbearing potential not using effective methods to prevent pregnancy.
- The safety and effectiveness of gemcabene has not been established in children and juvenile toxicity studies are underway but not yet completed.
- 2-year carcinogenicity studies are ongoing and therefore potential for carcinogenic activity is still not known.

Risks from the procedures in the protocol:

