7 STUDY INTERVENTION DISCONTINUATION AND PARTICIPANT DISCONTINUATION/WITHDRAWAL

7.1 DISCONTINUATION OF STUDY INTERVENTION

Discontinuation from gemcabene does not mean discontinuation from the study, and remaining study procedures should be completed as indicated by the study protocol. If a clinically significant finding is identified (including, but not limited to changes from baseline) after enrollment, the investigator or qualified designee will determine if any change in participant management is needed. Any new clinically relevant finding will be reported as an adverse event (AE).

The data to be collected at the time of study intervention discontinuation (Early Termination Visit) will include the following:

- Blood tests
- MRI
- Vital signs, physical measurements, and a physical examination
- Questionnaires (Food Frequency Questionnaire, PROMIS Questionnaires, Beverage Questionnaire, Physical Activity Assessment)
- Urine collection and pregnancy test (in WOCBP)
- Adverse event and concomitant medication review

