8 STUDY ASSESSMENTS AND PROCEDURES

8.1 EFFICACY ASSESSMENTS

Study Procedures:

Central Lab Tests

The primary and secondary outcomes listed below will be batched and measured at a central lab. At each indicated study visit (see SOA), plasma will be collected, aliquotted and frozen within 2 hours of collection and shipped to the Cardiovascular Research Lab at the Atlanta VA. After all study visits are completed and samples are obtained for all participants, the following tests will be measured:

- Lipid panel (TG, CHOL, HDLc, LDLc)
- Apolipoprotein panel (apoA-1, apoB, apoC-II, apoC-III, apoE)
- hsCRP
- Liver function panel (AST, ALT)
- Diabetes panel (GLU, INS, NEFA)
- Pharmacokinetics (Week 2, Week 6, Week 12 and in sub-study participants at Emory 0, 2, 4 and 6 hour)

Local (safety) labs

In order to assure the safety of participants at the time of their participation in the study, the labs listed below will be performed locally at the time of the visits and reviewed by the study staff. For those labs that are measured by the local lab and by the central lab (ALT, AST, Glu, Lipids) the central lab measurements will be used for outcome analysis. In the case that a central lab is missing, this will be noted and if the local lab is available it will be used. (also see SOA).

- CMP (includes Glu, BUN, Creatinine, Lytes, Calcium, Total Protein, Albumin, Alk Phos, AST, ALT, Total Bilirubin)
- CBC (includes WBC, RBC, HGB, HCT, MCV, MCH, MCHC, RDW, PLT)
- GGT
- CPK
- Lipid profile (includes cholesterol, triglycerides, HDL, LDL, and VLDL)
- HbA1c
- UA (includes chemical analysis, blood, nitrites, leukocyte esterase, protein)
- PT/INR

Imaging:

Limited MRI (no contrast) of the abdomen to measure percent hepatic steatosis and the liver multiscan. The Resonance Health (HepaFat) scan will be used for liver fat and pancreatic fat and the Perspectum Liver Multiscan (LIF and cT1 scores) will be used for inflammation and fibrosis. Body composition will be assessed by AMRA Medical AB (AMRA).

Patient reported outcomes:

PROMIS questionnaires fatigue, anxiety and depression (see Appendix B)

Study Procedures by Visit:

Please refer to Section 1.3 Schedule of Activities for additional visit details

Unscheduled Visits:

- Repeat MRI or labs
- Rescreening Visit
- Repeat ALT (for screening)
- Early Termination Visit

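### No scheduled blood count falls between first dose and Week 12, so no planned test would find an asymptomatic hemoglobin fall while the stop rule could still act

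*Combined protocol and SAP*

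**What the plan says.** Two hemoglobin triggers apply. Under 8.2 and 10.1.2, a drop of more than 1.5 g/dL from baseline leads to repeat hematology, a reticulocyte count and a clinical review. Section 10.1.2 adds the stop: "If hemoglobin falls >3.0 g/dL without any clear cause, then the investigator should discontinue the investigational product". Hemoglobin is then followed until it is back to within 1.0 g/dL of baseline, and the investigator may consider a restart.

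Section 2.3.1 gives the reason for watching it: "important potential risks are liver findings, hemoglobin decrease, BUN and creatinine increase and myalgia". The same section adds that clinical decreases have been small, were not statistically significant, and also occurred on placebo.

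On timing, Table 2 marks the CBC at Screening, Week 12, Early Termination and the three long-term visits. Table 3 allots 4 mL for it at Screening, Week 12 and those long-term visits, and prints dashes at Baseline, Week 2 and Week 6.

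On the laboratory, 10.1.2 states "Hemoglobin will be assessed by central laboratory evaluation". Table 2 and Section 8.1 list the CBC among the local safety tests. Section 8.1 says of the central panel: "After all study visits are completed and samples are obtained for all participants, the following tests will be measured". The list that follows contains no hematology.

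**The concern.** A rule that withdraws drug because of a laboratory value needs that value while the child is still taking drug. Here the first routine hemoglobin after Day 1 comes at the visit where dosing ends. By then the result can prompt follow-up, but there is no exposure left to prevent. Creatinine, by contrast, is part of the metabolic panel drawn at every clinic visit, so its trigger has data throughout dosing.

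This is the first study of the drug in children, and the protocol itself chose hemoglobin as something to act on. What is at stake is the safety of individual participants during 12 weeks of dosing. Efficacy inference is not involved.

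Two wording problems add to the gap. The 1.5 g/dL trigger is a change from baseline, yet no CBC is drawn at Baseline, and the plan does not say that the Screening value stands in for it. In addition, 10.1.2 sends hemoglobin to a laboratory whose listed tests do not include it and whose panel is run only after every participant has finished.

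**Working it through.** **Inputs.** Table 2 (which visits have a CBC; its footnotes place hemoglobin in the CBC and not in the metabolic panel, CMP); Table 3 (volumes); Table 1 (visit days and windows); 6.1.2 (first dose on Day 1); 4.2 (4 to 6 weeks between screening and first dose); 7.1 (Early Termination).

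**Step 1. Are the empty CBC cells real?** Blank cells in a converted table could be an extraction fault, so Table 3 was rebuilt from its rows (mL):

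| Visit | CMP | CBC | PT/INR | HbA1c | Sum | Printed subtotal |
|---|---|---|---|---|---|---|
| Screening | 8.5 | 4 | 2.7 | 4 | 19.2 | 19.2 |
| Baseline | 8.5 | 0 | 2.7 | 4 | 15.2 | 15.2 |
| Week 2 | 8.5 | 0 | 0 | 0 | 8.5 | 8.5 |
| Week 6 | 8.5 | 0 | 2.7 | 0 | 11.2 | 11.2 |
| Week 12 | 8.5 | 4 | 2.7 | 4 | 19.2 | 19.2 |
| Each long-term visit (3) | 8.5 | 4 | 2.7 | 4 | 19.2 | 19.2 |

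The CBC row gives 5 × 4 = 20 mL, as printed. The safety subtotals add to 130.9 mL, and 130.9 + 75 (central subtotals) = 205.9 mL, also as printed. The figures agree only if no CBC is drawn at Baseline, Week 2 or Week 6.

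**Step 2. How long is the gap?**
- First dose to Week 12: 85 − 1 = 84 days. With the ±10-day window, 75 − 1 = 74 to 95 − 1 = 94 days.
- Screening CBC to Week 12: 28 + 84 = 112 to 42 + 84 = 126 days nominally; with the Week 12 window, 28 + 74 = 102 to 42 + 94 = 136 days.
- Clinic visits after first dose and before Week 12 that have a CBC: 0 of 2.

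**Step 3. Does the Early Termination CBC close it?** Section 7.1 introduces that visit with "The data to be collected at the time of study intervention discontinuation (Early Termination Visit) will include the following". Its CBC is taken because drug is being discontinued, so it cannot be what prompts the discontinuation.

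**Step 4. What would added CBCs change?** With counts at Baseline, Week 2 and Week 6, the nominal intervals become 15 − 1 = 14, 43 − 15 = 28 and 85 − 43 = 42 days. The longest interval without a scheduled hemoglobin falls from 84 to 42 days. At the extreme of the Week 6 and Week 12 windows it is 95 − 33 = 62 days.

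**Step 5. Blood volume.** 3 × 4 = 12 mL per child; 205.9 + 12 = 217.9 mL; 12 / 205.9 = 5.8%.

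**The case against.** The strongest reply is that hemoglobin is not unwatched and that a large fall is unlikely. Adverse events and vital signs are reviewed at Weeks 2 and 6. Section 8.1 allows unscheduled repeat labs. The liver-injury plan in 8.3.10 refers to eosinophilia, so a blood count might be drawn for that reason. Section 10.1.2 separately stops drug for "an AE of grade 3 that is probably or possibly related to study drug" and for any event of grade 4 or higher. The Week 12 CBC can still start the work-up and follow-up. All of this stands, and it limits the point to falls without symptoms: nothing in the plan prompts a count in a child who feels well.

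The risk evidence is also modest. Section 2.2 reports lower hemoglobin in rats, but together with 25–46% body-weight decreases at 30–300 mg/kg/day; here the dose is at most 300 / 60 = 5 mg/kg/day. The monkey red-cell changes were mild and present at all doses, including the 30 mg/kg/day that the protocol gives as the no-adverse-effect level. A reader might infer a thin exposure margin from the statement in 2.2 of up to 4 times the expected exposure in a 52-week monkey study. That sentence concerns peroxisomal structures, and the documents do not tie it to the red-cell finding, so the inference is not used here.

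Finally, the Version 1.1 entries in 10.4 show that the Week 12 CBC and the stopping rules were both added at the FDA's request, so the timing may have been deliberate. That is fair background, but it does not supply a value during dosing.

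**Conclusion.** The point holds in this form: no scheduled test would detect an asymptomatic hemoglobin fall during the 84 days of dosing (74 to 94 with the Week 12 window), when stopping drug could still help. It rests on Tables 2 and 3 as printed, which agree with each other and with Table 3's arithmetic, and on dosing ending at the Week 12 visit.

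Three stronger readings are not supported. First, a reader might infer that the stop rule can never operate; unscheduled testing could trigger it, so the gap is one of scheduled detection. Second, a reader might infer that the recheck steps after a restart make the rule unworkable by a certain day; restart is optional, and the protective step is the stop. Third, a reader might infer that a large fall is to be expected; the clinical experience that the protocol describes points the other way.

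The conflict between the central and local laboratory and the unnamed reference value are real, and they belong in the same correction. The primary endpoint and its analysis are unaffected. This should be fixed because a child-safety rule that the protocol already contains can be given its data at little cost.

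**What to change.** In one amendment:

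1. In Tables 2 and 3, add a CBC at Baseline, Week 2 and Week 6, from blood draws already scheduled.
2. In 8.2 and 10.1.2, name the Baseline CBC as the reference for hemoglobin changes.
3. In 10.1.2, replace the central laboratory with the local laboratory, so that results arrive in time to act on.

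The cost is the amendment and three 4 mL samples per child. Visit totals without the sub-study rise from 29.2 to 33.2 mL at Baseline, 15.5 to 19.5 mL at Week 2 and 28.2 to 32.2 mL at Week 6. For sub-study children, Baseline goes from 85.2 to 89.2 mL. No visit or needle stick is added. The documents do not show that three counts are the minimum needed; if blood volume were limiting, the sponsor could justify fewer, provided at least one falls early enough in dosing for a stop to matter.
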